
**C.3. Participants.** Participants will be low-income mothers/infants (6mo at enrollment) *who are already receiving services from our HVP partner (Figure 6)*. Thus, study enrollment does not require that we recruit more families than our HVP partner is already enrolling. Mothers are enrolled in HVP services through outreach and screening pre-partum, in English or Spanish, at community health centers and hospitals. In order to be eligible mothers must meet a number of (but not all) risk criteria (e.g., low-income, housing instability). Enrolled mothers are matched to a home visitor (nurse) based on culture and language. **Recruitment.** Assessment workers (distinct from home visitors delivering services) who enroll families into services will introduce the study to mothers and obtain written consent. They will clarify with mothers that their refusal to participate in the study will not affect their receipt of any other services provided by the HVP. In our experience, families feel comfortable refusing if they are not willing to participate. Mothers/infants will be ineligible if they have any of the following conditions: eating disorders (e.g., bulimia nervosa), schizophrenia, and obesity-related syndrome (e.g., Prader Willi). Participants enrolled in a weight-loss program will be ineligible. Based on our pilot work, we expect to recruit 70% Hispanic/Latino, 13% African American, 8% White, 5% American Indian/Alaskan, 4% mixed race. **Retention.** We have learned a great deal about retention through our pilot work. For instance, most attrition from HVP services occurs in the first six months of services. Therefore, to maximize retention, mothers will be invited to participate in the study *after six months of home visits*. The unique relationship between home visitors and mothers facilitates subsequent retention, as many of these mothers are socially isolated and home visitors are important confidants and supports. We will use multiple strategies that are effective for high-risk populations to further retain the study sample: (1) gift cards of \$25 at each data collection, with all incentives paid after each assessment; (2) frequent contacts to maintain engagement and foster open communication; (3) quarterly newsletters to update subjects about study activities; (4) acknowledging birthdays and milestones; (5) reminder phone calls the day before the weekly visits and assessment sessions. **Randomization.** Randomization will be at the level of home visitors, who deliver the HVP (cluster randomization). Home visitors who serve mothers that are participating in the proposed study will be randomly assigned to deliver either HVP only or HVP+COPE. Potential concerns with randomizing by home visitors are feasibly addressed in this study. First, the likelihood of

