**C.4. Intervention Arms (Table 4).**

**HVP curriculum.** Our HVP partners are two of 400 nationwide *Healthy Families America* (HFA) sites/chapters, housed at Antelope Valley Partners for Health and the Antelope Valley Children’s Bureau. The HFA model meets the DHHS criteria for an “evidence-based early childhood home visiting service delivery model” (See <http://homvee.acf.hhs.gov>). HFA services begin prenatally and continue until children are 2-5yo depending on the HVP model. The curriculum focuses on strengthening parent-child relationships and family functioning, promoting positive child development, and linkage to community resources (e.g., medical providers, financial/housing assistance, childcare, substance abuse treatment, community programs).

**HFA accredited home visitors** (Nurses) are matched to families on cultural background and language (English or Spanish), to provide culturally sensitive services. Home visitors are selected because of their personal characteristics (e.g., non-judgmental, compassionate, ability to establish a trusting relationship), their experience working with culturally diverse communities, and their skills to do the job. HFA home visitors are expertly trained and experienced in handling situations encountered while working with at-risk families. They receive training in cultural competency, substance abuse, reporting child abuse, domestic violence, and linkage to services in their community. Home visiting staff also receive intensive training specific to their role (e.g., identifying at-risk families, standardized assessments, phlebotomy, mental health referrals, promoting preventive health care, utilizing creative outreach efforts, establishing and maintaining trust with families, building upon family strengths, developing individual family support plans, teaching parent-child interaction, managing crises). Staff also receive weekly supervision, ongoing developmental training, and have limited caseloads (10-15 families) to meet their families’ needs.

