**Maternal weight & waist circumference.** Weight and height will be measured by Assessment Workers in participants' homes using an electronic scale (Model BWB-800S, Tanita, Portage, MI) and stadiometer (Model PE-AIM-101, Perspective Enterprises) according to standard procedures. Subjects will remove shoes, belts, and heavy outerwear and empty pockets. We will measure height in duplicate and if measurements are not within 0.5 cm, we will obtain a third measurement. The mean of all measurements will be used to calculate BMI. Waist circumference will be measured at the umbilicus to the nearest 1 mm using a non-stretch measuring tape. Maternal obesity prior to pregnancy will be derived from pregravid BMI (recall during pregnancy at recruitment). Gestational weight gain will be defined as the last weight obtained before delivery minus the pregravid recalled weight or the weight recorded at the first prenatal visit during the first trimester using electronic medical record data.

**Maternal diet & activity.** Mothers' dietary intake and activities will be assessed using several items from NHANES (2017), including intake of fruits and vegetables, fried foods, and sugary-sweetened beverages, and time mothers engage in moderate physical activity.

**Maternal social networks & support.** Using egocentric social network methods and EgoWeb software (<http://www.rand.org/methods/egoweb.html>, developed with PI [name]), we will assess the characteristics of the social actors (people, organizations) and relationships that surround mothers. Using standard name generator items, participants are asked to identify 20 important adults in their lives, and then report on the attributes of each person (demographics, health attributes/behaviors) and types of relationships they share. Relationship characteristics of interest include how they know the person (e.g., family, friend from a community program, etc.), frequency of interaction, and provision of support for health behaviors (e.g., encouragement for or co-engagement in specific behaviors). *Social Support measures from the PROMIS database* will be used to assess emotional and instrumental support, and social isolation. Egocentric network data is used to compute network composition variables (e.g., proportions of family/friends in the network), and variables that represent

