## C.6. Analytic Plan.

**General strategy.** Three waves of data will be collected (baseline/enrollment, 6 and 12- months of intervention). Analyses will be carried out according to the intention-to-treat rule consistent with standard practice in most clinical trials. We will conduct standard statistical diagnosis and descriptive statistics of demographic and background variables, and examine frequencies for reasonableness, sparseness (categorical data) and non-normality (continuous variables) of the data. Missing data will be addressed using multiple imputation and/or full information maximum likelihood estimation. Psychometric properties of the study scales will be investigated to ascertain appropriate validity and reliability. Preliminary analyses will test group equivalence on baseline characteristics. Categorical methods of analysis (e.g., cross tabulations, chi-square) will be used for discrete data while *t*-tests will be used for continuous data to test the comparability of the prevention arms. Factors found to be different at baseline will be adjusted for in subsequent analyses. The following **covariates** will be entered in all analyses: home visitor, home visitor experience (years), number of visits, household composition, race/ethnicity, acculturation, mother's age, medical history/gestational diabetes, post-partum depression.

**Social network analysis (SNA).** Network data will be analyzed using SNA packages in R (e.g., SNA, igraph) to produce visualizations and statistics that summarize the characteristics of each mothers' network. We will compute the following network statistics: the proportion of network members that provide specific types of health relevant support, and that engage in specific health behaviors; and the density of supportive relationships within each network (i.e., the number of supportive relationships among network members that are reported, as a proportion of the total number of possible supportive relationships where all network members provide support). These statistics will be computed for each assessment period (as well as change statistics across periods), and included in the analyses, as described below.

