## PROTECTION OF HUMAN SUBJECTS

### A. Participants

This comparative effectiveness research involves the enrollment of 300 mothers/infants for a final effective sample of 200 mothers and their infants (age 6mo at enrollment).

**Inclusion of women.** Women are represented by mothers and female infants, which will be about half of the infant sample. Based on our projected effective sample of 200 mothers and their 200 infants (N=400), we anticipate that 75% of our sample will be women (100 children + 200 mothers = 300).

**Inclusion of racially and ethnically diverse families.** The families enrolled in the Home Visiting Program (HVP) from which the sample is drawn is culturally, racially and ethnically diverse, reflecting the population of low-income families enrolled in home visiting services in the Antelope Valley, CA area. Based on our HVP partner (Healthy Families America site in Southern California: Antelope Valley Partners for Health and Children's Bureau) clients' demographics and on our pilot work, we anticipate the following ethnic and racial distribution: 70% Hispanic/ Latino, 13% African American, 8% White, 5% American Indian/Alaskan, and 4% mixed/other race.

It is important to note that Health Families America (HFA) home visitors are matched to families based on language and cultural background. Home visitors are rigorously trained to understand, acknowledge, and respect families' cultural differences. Home visitors are selected because of their personal characteristics (i.e. non-judgmental, compassionate, ability to establish a trusting relationship, etc.), their experience working with culturally diverse communities, and their skills to do the job.

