### C. Recruitment and Retention

**Participant recruitment.** Low-income mothers and their infants (N=300, for a final effective sample of 200) will be participants in the study. Active participants will be low-income mothers and their infants (6mo-old at enrollment) drawn from mothers who are enrolled in HVP services at the Healthy Families America site/chapter in Antelope Valley, CA. Home visitors providing the HVP services will introduce the study to mothers, and study Assessment Workers will obtain written consent. Home visitors will clarify with mothers that their refusal to participate in the study is not affecting the services they provide. In our experience from our pilot research, families feel comfortable to refuse if they do not wish to participate. Of note, 90% of families receiving *Healthy Families America* HVP services choose to enroll in enhancement studies when offered (i.e., when a module is added to the core curriculum and evaluated). These rates are consistent with our pilot work.

**Inclusion/exclusion criteria.** Participants will be ineligible if either parent and/or child have a Dx of eating disorders (e.g., Anorexia Nervosa), Schizophrenia or Obesity-related syndrome (e.g., Prader Willi). Participants enrolled in a weight-loss program will be ineligible.

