5. An external Data Safety Monitoring Board (DSMB), not connected to USC, UAB or the research project, will convene twice annually, via teleconference, to review the progress of the study, ensure adequate recruitment of minority subjects, and to monitor safety concerns. Key members of the research team will co-participate in the conference calls. The DSMB will consist of five to-be-named individuals from outside USC: (1) a home visitation program consumer (parent, most likely a mother) (2) a child services advocate; (3) a layperson; (4) a home visitation program stakeholder; (5) a health disparities researcher and (6) a mental health professional. The DSMB will meet by phone conference two times within each of the project's 5 years. Their function will be to review the progress of the study, ensure adequate recruitment of minorities into the sample, and monitor the study with respect to the safety and well-being of the research patients.
6. Safety officer. [name], DO is a pediatrician at the Antelope Valley Community Clinic. [name] will serve as safety officer on this project to ensure the protection, safety and satisfaction of mothers and staff throughout the many facets of the project. [name] will serve as contact-person to family participants, service providers, and all project staff to report problems or areas of concern regarding project implementation for resolution with investigators.

**Additional protections for pregnant women, human fetuses, and neonates involved in research.** This study involves parents and their infants (6mo at enrollment). This research does not involve women who are pregnant. If a mother becomes pregnant during the study, she will continue to receive HVP services, but she will not be involved in the study.

**Potential benefits of the proposed research to human subjects and others.** The potential benefits of this study include better management of postpartum weight-loss among mothers involved in home visitation programs and healthier growth trajectories for their infants. This study will also help researchers and professionals understand how home visitation programs can be used as a vehicle for early childhood obesity prevention. Participants will benefit by receiving a nutrition and physical activity module at no cost. Thus, the benefits of this project to the individual and society greatly outweigh the risks.

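### The covariates fixed for all analyses omit infant age and sex, although several infant outcomes are standardised for neither

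*Combined protocol and SAP*

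**What the plan says.** **Covariates (C.6, General strategy).** The variables that go into every analysis are "home visitor, home visitor experience (years), number of visits, household composition, race/ethnicity, acculturation, mother's age", followed by medical history with gestational diabetes, and post-partum depression. The mother's age is listed; the infant's age and sex are not. The same paragraph adds any factor that t-tests or chi-square tests show to differ between arms at baseline.

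**Models (C.6, Aim 1).** Multilevel regressions with the home visitor as cluster take in everyone with two or more measurements, whatever their timing. The baseline value of the outcome is a covariate. Effects are examined at each follow-up and then longitudinally.

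**Infant outcomes.** C.5 derives WHO weight-for-length and weight-for-age z-scores and takes growth as the change in weight-for-length z (WLZ). It also measures waist circumference and collects diet, feeding history and activity from the mother. The Power Analysis calls weight velocity the main child outcome, and the pilot results in B.7 give it in kg per month.

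**Entry timing.** C.3 states "Participants will be low-income mothers/infants (6mo at enrollment". Protection of Human Subjects repeats this in section A ("age 6mo at enrollment"), in section C ("low-income mothers and their infants (6mo-old at enrollment") and in section D. The retention paragraph of C.3 invites mothers once six months of visiting have passed, because most dropout occurs before then. On when visiting begins, C.3 says "Mothers are enrolled in HVP services through outreach and screening pre-partum" and C.4 says "HFA services begin prenatally and continue until children are 2-5yo depending on the HVP model", while the general description in B.6 (item e) also allows a start shortly after birth.

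**The concern.** In infancy, waist size, foods eaten, breastfeeding and active time all change quickly with age, and body size differs by sex. An infant model without these two variables leaves explainable variation in the residual. It also leaves the arm comparison open to whatever imbalance chance produces when only 30 visitors are randomised. What is at stake is precision and robustness. Randomisation already protects against systematic bias.

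The entry wording adds to this. It uses two clocks, infant age and time in service, gives no window around 6 months, and does not say which clock governs. The spread of infant ages at entry therefore cannot be read from the plan.

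**Working it through.** **Step 1. Which infant outcomes carry their own standardisation?**

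| Outcome | Age-standardised | Sex-standardised |
|---|---|---|
| Weight-for-age z (C.5) | yes | yes |
| Weight-for-length z (C.5) | no, indexed on length | yes |
| Weight velocity, kg/month (Power Analysis, B.7) | no | no |
| Waist circumference (C.5) | no | no |
| Diet, breastfeeding, activity (C.5) | no | no |

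Only weight-for-age z needs neither covariate. Breastfeeding is also a mediator in Aim 2, so the gap reaches the path models.

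**Step 2. Does anything else in the plan supply age or sex?**

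- *Time in the longitudinal model.* If every infant enters at exactly 6 months and is seen on schedule, time since entry equals age minus 6 and carries the same information. It does not capture spread in entry age or departures from the scheduled date, and no visit window is stated. Table 6 lists infant weight, length and waist at months 3 to 18, which is age 6 + 3 = 9 to 6 + 18 = 24 months. C.6 counts follow-ups at 6 and 12 months, which is age 12 to 18 months.
- *Number of visits.* This measures exposure to the programme and is a poor stand-in for age.
- *Baseline outcome.* It absorbs part of the entry-age effect, but not differences in age at follow-up.
- *Baseline-difference rule.* It could bring in age at entry or sex, but only after a significant test. It names neither, and it recovers no precision when the test is not significant.

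**Step 3. How much imbalance would the baseline rule let through?** The inputs are N = 200 and inflation factors (DE) of 1.4 to 1.8 from the Power Analysis. Those factors are reproduced by a cluster size of 9: 1 + 8 × 0.05 = 1.4 and 1 + 8 × 0.10 = 1.8. Equal arms are assumed.

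*Sex.* Protection of Human Subjects A expects 100 girls among 200 infants. Taking sex as unclustered, the standard error (SE) of the arm difference in the share of girls is 0.5 × √(4/200) = 0.071. A two-sided 5% test flags only gaps above 1.96 × 0.071 = 0.14, or 14 percentage points.

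*Entry age.* The documents give no spread, so a uniform spread over an assumed range is used: SD = range/√12 and SE = SD × √(4 × DE/200). Applying the plan's inflation factors to age is also an assumption.

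| Assumed range (months) | SD | SE, DE 1.0 | SE, DE 1.4 | SE, DE 1.8 | 1.96 × SE (DE 1.0 to 1.8) |
|---|---|---|---|---|---|
| 1 | 0.29 | 0.041 | 0.048 | 0.055 | 0.08 to 0.11 |
| 3 | 0.87 | 0.122 | 0.145 | 0.164 | 0.24 to 0.32 |
| 6 | 1.73 | 0.245 | 0.290 | 0.329 | 0.48 to 0.64 |

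The gain in precision cannot be given as a number, because the documents report no association of age or sex with any outcome. If the two variables explain a share R² of the remaining variance, adjustment removes that share.

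**Step 4. The two entry clocks.** Let s be the month of the first visit relative to birth. If mothers are invited exactly at six months of visits, infant age is 6 + s. If they are invited when the infant is 6 months old, months of visits are 6 − s. Start times are assumed.

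| s | Age if invited exactly at 6 months of visits | Months of visits when infant is 6 months |
|---|---|---|
| −6 | 0 | 12 |
| −3 | 3 | 9 |
| −1 | 5 | 7 |
| 0 | 6 | 6 |
| +1 | 7 | 5 |
| +2 | 8 | 4 |

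If six months is a minimum, every prenatal starter meets both rules at infant age 6 months. A mother who starts after birth cannot: a start at one month gives only five months of visits by then.

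**The case against.** The strongest defence is that the main growth measure is a z-score, that the baseline outcome is a covariate, that visitors are randomised, and that baseline differences are to be adjusted for. This limits the point. Weight-for-age z needs no change, no systematic bias arises, and even a six-month spread in entry age gives an SE of only 0.24 to 0.33 months for the arm difference. It does not cover the unstandardised outcomes, and a test-driven rule does not replace covariates fixed in advance.

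Three stronger readings are tempting, and the documents do not support them.

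- *A reader might infer that the two entry rules cannot both hold for mothers who begin visits before birth.* The reason given in C.3 is to wait out early dropout, which suits a minimum. Under a minimum, prenatal starters are the mothers for whom both rules hold.
- *A reader might infer that infants enter at widely different ages.* The 6-month age is stated four times. If it governs, entry age is nearly constant and prior service time varies instead (6 to 12 months for starts up to 6 months before birth). No distribution of start times is given.
- *A reader might take the phrase "recall during pregnancy at recruitment" in C.5 as a third entry clock, at odds with "This research does not involve women who are pregnant" in Protection of Human Subjects D.* The phrase concerns recalled pre-pregnancy weight and fits recruitment into the home visiting programme. Section A says that weight comes from the programme partner.

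Figure 6, the enrolment flow, is not shown in the text available and may clarify the timing.

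**Conclusion.** The point holds as a free improvement to the analysis plan. Infant age and sex are missing from the covariates fixed for all analyses, while most infant outcomes other than the z-scores depend on age or sex, and measurement times are left open. The benefit is precision and protection against chance imbalance. Under the plan's own numbers, the baseline rule would leave a gap of up to about 14 percentage points in infant sex unadjusted. Under an assumed 3-month uniform spread, it would leave a gap of up to 0.24 to 0.32 months in mean entry age. If all infants enter very close to 6 months and are seen on schedule, the age term adds little and the sex term still helps.

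The entry wording is a secondary clarification. The two clocks agree for prenatal starters only if the service-time rule is a minimum, and they conflict for any mother starting after birth. That group rests on the general description in B.6; C.3 and C.4 describe services as beginning before birth.

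**What to change.** In C.6 (General strategy and Aim 1), prespecify infant age at assessment, computed from actual dates, and infant sex as covariates in every infant model whose outcome is not already a z-score standardised for both. This includes infant and breastfeeding equations in the path models for Aims 2 and 3. For weight-for-length z, add age at assessment only. For change or velocity outcomes, say whether age enters at the start of the interval, the end, or both. State the form of the age term in advance.

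In C.3 and in Protection of Human Subjects A, C and D, reconcile the service-time and infant-age wording. State which rule governs, whether six months of visits is a minimum, the age window around 6 months, and how mothers who start visits after birth are handled.

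The cost is a few sentences and one or two extra parameters per infant model. No new data are needed, since the WHO z-scores already require age and sex. A stated window may make a few families wait or fall outside it.
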